Protocol: AAAF1797

Principal Investigator: [name]

Title: Randomized controlled trial of Vitamin D Repletion Regimens in Primary Hyperparathyroidism

Study Purpose and Rationale:

Vitamin D deficiency is very common in the setting of PHPT, and leads to higher PTH levels. In this study, we will investigate the impact of two different vitamin D repletion regimens over a six month period in patients with PHPT and concurrent vitamin D deficiency. We hypothesize that vitamin D repletion ameliorates the extent of hyperparathyroidism and improves biochemical, microarchitectural and biomechanical features of the disease. In addition, we will show that vitamin D can be repleted safely in patients with PHPT. This would be of great importance to the many physicians treating patients with PHPT today, who are being advised to replete vitamin D in these patients without any clear guidelines as to how best to do so.

Study Design:

40 patients with PHPT and vitamin D deficiency (25OHD less than 30 ng/ml) will be enrolled and randomized 4:1 to two different vitamin D repletion regimens. Randomization to treatment will use randomly permuted blocks. Our first group will receive 2 capsules of 10,000 IU of vitamin D once per week for the first month and then 1 capsule of 10,000 IU of vitamin D once per week for the remaining five months which should replete vitamin D deficiency and decrease PTH (our primary end-point). Control subjects (Group 2) will take 2 capsules of the placebo once per week for the first month and then 1 capsule of the placebo once per week for the remaining five months. All subjects will receive 400 IU of vitamin D each day, either in the form of a multivitamin or by itself, for the entire study. Our protocol provides 400 IU of vitamin D per day for control subjects because we felt that ethically it would not be appropriate to withhold all vitamin D from this group. A 400 IU dose is expected to raise serum 25-OHD levels minimally (2-3 ng/ml) thus allowing this cohort to serve as a valid control group ¹.

Study drug will be dispensed at the first visit as appropriate to randomization. Participants will be instructed on and receive a printed medication administration schedule. They will be advised to begin taking their study drug immediately, and up to 500 mg of supplemental calcium but no additional vitamin D. They will be instructed about events that could be related to hypercalcemia or hypercalciuria: nephrolithiasis, nausea, vomiting, polyuria/polydipsia, or fractures.

The study will have a 6 month design, which will allow us to capture our treatment groups before and during the process of becoming vitamin D replete. Many PHPT patients are monitored without surgery for years and thus determining the safety and effect of maintaining adequate 25-OHD levels is imperative.

No vitamin D toxicity data exist in patients with PHPT. Available data in normal subjects are of limited applicability to patients with PHPT who are hypercalcemic and often hypercalciuric at the outset. However, in normal subjects hypercalcemia does not occur unless serum 25-OHD levels are above 150-200 ng/ml. The Food and Nutrition Board has set a safe tolerable upper intake level of 2000 IU daily for vitamin D3 and 2400 IU as the no-observed adverse-effect level. More recent clinical trial data suggest that these assessments are extremely conservative ². It should be noted that none of the patients

treated by Grey et al. achieved a 25-OHD level above 50 ng/ml, and their mean increment in 25-OHD was 19 (range 6-37 ng/ml). However, because PHPT patients may be more susceptible to adverse effects due to their baseline elevations in serum and urinary calcium, the careful monitoring we propose is essential to allow conclusions about safety of repleting vitamin D in PHPT. In addition, because of this concern, we will exclude any patient with: serum calcium greater than 11.5 mg/dL; urine calcium greater than 350 mg/dL per day; active nephrolithiasis or nephrocalcinosis. We will also compare the percentage of participants who achieve a 25-OHD level above 30 ng/ml in each group, and assess the changes in serum and urinary calcium, 25-OHD and 1,25-OH₂D among groups. We will describe the time course of the normalization of 25-OHD levels in the treatment group and evaluate whether the level of vitamin D or acuity of the change in vitamin D is predictive of adverse events. We plan to analyze the data on an intent-to-treat basis, but will also do a secondary per protocol analysis based upon final vitamin D level in order to estimate achievable PTH reduction in regimen compliant subjects. Finally, we will assess patients for the development of safety outcomes. Participants whose serum calcium concentration rise above 12 mg/dL or develop nephrolithiasis (evaluation of clinical complaint) will be withdrawn. Although we will also monitor and compare the number of participants in each group whose urinary calcium level exceeds 400 mg/day, these individuals will not be withdrawn as explained in the Data and Safety Monitoring section. The frequency of patients with these outcomes at each time point will be compared among groups. We expect that the treatment regimen will be effective in achieving a vitamin D level above 30 ng/ml, while the 400 IU control group will not reach this threshold. The issues assessed here will therefore be of great value in formulating recommendations for vitamin D treatment, a key research goal of the new Consensus Guidelines, and an imperative for clinicians treating PHPT patients.

Describe how participants will be recruited:

Patients with primary hyperparathyroidism will be recruited by physician referral from the population of patients seen in the Metabolic Bone Diseases Unit, Endocrine Clinic, and the Surgical Endocrine Unit. During a medical visit, eligible patients will receive information about the study and study procedures by their physician. Those patients interested in the study will give their permission to have their contact information sent to the study coordinator and PI for follow-up. Patients who do not want to hear more information about the study will not be contacted. Those patients who agree to hear more information about the study will be contacted by the PI or the study coordinator. The patient will learn more about the study, study procedures, and the consent form. Those who agree to participate will have the consent form mailed to them for further review. During their first visit, the study coordinator, or the physician, will go over the consent form and answer any other study related questions, the participant will then sign the consent form. The availability of patients from both the medical and surgical services at Columbia University Medical Center (CUMC) over the funding period should provide ample opportunity for us to enroll patients.

Statistical Procedures:

The primary statistical analysis of the 6-month endpoint will be an intent-to-treat (ITT), "as prescribed", ANCOVA assessment of between group differences in log-transformed serum PTH level adjusted for baseline serum PTH and the covariates listed below. The primary ITT analysis will be repeated with actual cumulative vitamin D intake entered as a continuous time-dependent covariate to estimate the time course of the "as treated" decrease in PTH level. Analysis of the longitudinal growth curve of each

measure will use linear mixed models for repeated measures to assess the fixed effects of vitamin-D repletion regimen, time, regimen time interaction, random effects for intercept and standard covariates; and a covariance structure fit prior to the hypothesis test. Average time to achieve a 25-OHD level of 30 for the two vitamin-D repletion regimens will be estimated with a Cox proportional hazards model. Power and sample size calculations assume PTH is analyzed in log units, unequal sample sizes in the two groups, unequal variances in the two groups, a type I error rate of 0.05, 80% power and a two-tailed T-Test of the post-treatment PTH levels. A reduction in the treated group from 149 ± 64 ng/ml to 85 ± 48 pg/ml is larger than our original estimated effect size but consistent with the data available from our cross-sectional study for patients with 25OHD 30 ng/ml, respectively. Given the above assumptions and a desired 4:1 treatment allocation ratio, a sample size of 40 distributed 32 vs 8 meets our power goal (calculated with harmonic mean sample size of 13 per group). The analysis of safety event rates will include Fisher's Exact comparisons of between-group differences in the number of patients with hypercalcemia and/or hypercalciuria; and a Cox proportional hazards assessment of time to first AE adjusted for standard timeindependent covariates and time-dependent cumulative vitamin D dosage will be used to estimate the contribution of vitamin D to the development of the safety events. Assessments of safety events will be conducted to relate the onset of safety events to baseline vitamin-D levels, to the ramp of vitamin-D level increase and peak available vitamin-D level at time of event (to the extent known). Standard covariates for all analyses include season, weight, serum calcium and age. All power and sample size calculations based on SAS Power and Sample Size 3.1 (SAS Institute, Cary, NC).

References:

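### Two secondary analyses do not match their stated aims: final 25-OHD does not identify regimen-compliant patients, and a 6-month ANCOVA cannot give an as-treated time course

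*Combined protocol and SAP*

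**What the plan says.** **Per-protocol analysis (Combined protocol and SAP, Study Design).** Besides the ITT analysis, the plan announces a "secondary per protocol analysis based upon final vitamin D level in order to estimate achievable PTH reduction in regimen compliant subjects". It gives no cut-off and does not say how controls enter the set.

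The same section sets the regimens. The treated arm takes "2 capsules of 10,000 IU of vitamin D once per week for the first month and then 1 capsule of 10,000 IU" weekly for the remaining five months. For the other arm, "Control subjects (Group 2) will take 2 capsules of the placebo once per week for the first month", then one weekly. In addition, "All subjects will receive 400 IU of vitamin D each day". Entry requires 25-OHD below 30 ng/ml. Controls are expected to rise by 2-3 ng/ml and not to reach 30. Participants are told to take no vitamin D beyond what the study provides. For patients treated in an earlier cited study, "their mean increment in 25-OHD was 19 (range 6-37 ng/ml"), and none exceeded 50 ng/ml.

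**As-treated analysis (Statistical Procedures).** "The primary statistical analysis of the 6-month endpoint will be an intent-to-treat (ITT") ANCOVA of log PTH. Then: "The primary ITT analysis will be repeated with actual cumulative vitamin D intake entered as a continuous time-dependent covariate", with the aim of estimating the time course of the as-treated fall in PTH. A separate longitudinal analysis uses "linear mixed models for repeated measures to assess the fixed effects of vitamin-D repletion regimen, time, regimen time interaction", a random intercept and the standard covariates, which are season, weight, serum calcium and age. Intake is not among the listed terms.

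**The concern.** In each case the analysis as specified answers a different question from the one it is said to answer.

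(a) The per-protocol result would be read as the PTH reduction available to patients who take the regimen. Selecting on final 25-OHD instead describes PTH in patients who reached a given level. Some full compliers miss that level and some partial compliers reach it, depending on where they started and how they respond. For controls the marker cannot show whether the placebo capsules were taken. Because the rule is unstated, it could also be settled after the data are seen, with only 8 controls in the comparison.

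(b) The as-treated analysis promises a time course from a model that contains a single time point. An analyst who follows the text literally cannot produce the stated output, and one who departs from it must choose the model unguided.

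**Working it through.** **What the plan's own figure covers.** The plan states no number for either secondary analysis. Its sample size belongs to the primary analysis and reproduces: the harmonic mean is 2 x 32 x 8 / 40 = 12.8, rounded to 13. A Welch calculation with ln(149/85) = 0.561 and log SDs taken as 64/149 and 48/85 gives 82% power at 32 vs 8. Nothing below changes that.

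**(a) Step 1: direct arithmetic.** The plan gives no cut-off, so 30 ng/ml is assumed, being the threshold it uses elsewhere.
- A full complier starting at 10 with the cited mean rise of 19 ends at 29 and is excluded.
- A patient starting at 25 who takes half the capsules, with half that rise (an assumption), ends at 25 + 9.5 = 34.5 and is kept.
- A control rising 2-3 reaches 30 only from a baseline of about 27-28 or more, so few or none of the 8 would qualify.

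**(a) Step 2: fixed baselines.** Increments are normal with mean 19, truncated to the cited limits 6 and 37, with assumed SD 5 to 9. Half intake gives half the increment.

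| Baseline (ng/ml) | Full compliers at or below 30 | Half-intake patients above 30 |
|---|---|---|
| 10 | 52-58% | 0% |
| 15 | 21-28% | 1-10% |
| 20 | 3-9% | 42-48% |
| 25 | about 0% | 91-97% |

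**(a) Step 3: a spread of baselines.** Baseline is normal with SD 6, truncated to 0-30; full-intake rise is 19 with SD 7 or 4; final = baseline + intake fraction x rise. All SDs and baseline means are assumptions. The means are those before truncation; the 25 case averages 22.9 afterwards.

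| Baseline mean | Full compliers excluded, rise SD 7 | Rise SD 4 |
|---|---|---|
| 15 | 33% | 29% |
| 20 | 17% | 11% |
| 25 | 8% | 3% |

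At baseline mean 20, about 45% of half-intake patients are kept. If 80% of the 32 treated comply fully and 20% take half, exclusions in the SD 7 case are 25.6 x 0.172 = 4.4 full compliers and 6.4 x 0.55 = 3.5 half-intake patients. More than half of those excluded would have been fully compliant.

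**(a) Step 4: bias under no treatment effect.** Let r be the within-arm correlation of 6-month log PTH with final 25-OHD, at baseline mean 20 and rise SD 7. The first figure compares treated patients at or above 30 with all controls; the second compares them with controls below 30.

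| Log SD | r = 0 | r = -0.1 | r = -0.3 |
|---|---|---|---|
| 0.5 (no baseline adjustment) | 0 | -0.015 / -0.024 | -0.047 / -0.073 |
| 0.357 (baseline-PTH correlation 0.7 assumed) | 0 | -0.011 / -0.017 | -0.033 / -0.051 |

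The spurious fall is thus 0-7%, or up to about 5% with baseline adjustment. The planned fall is 1 - 85/149 = 43%.

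**(b) Step 1: structure.** A 6-month ANCOVA has one PTH outcome per patient. Cumulative intake at that visit is also one number per patient. Time does not vary in the data, so no coefficient can describe change over time.

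**(b) Step 2: intake alongside arm.** With 4 weeks at the higher dose and 22 at the lower, assigned capsule intake is 4 x 20,000 + 22 x 10,000 = 300,000 IU in the treated arm and 0 in controls. The daily supplement adds 400 x 182 = 72,800 IU in both. Adherence is drawn uniformly over the stated range (assumed), and the variance inflation factor for arm with intake is 1/(1 - R²), computed before R² is rounded.

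| Adherence | R² | VIF |
|---|---|---|
| 90-100% | 0.995 | about 210 |
| 80-100% | 0.979 | about 47 |
| 60-100% | 0.902 | about 10 |
| 40-100% | 0.760 | about 4 |

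At good adherence, intake and arm can hardly be separated if both stay in the model.

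**The case against.** **Final 25-OHD is not uninformative.** It is objective and carries some information on intake in the treated arm. A reader might infer that it is useless in controls. The documents do not support that: participants may not take outside vitamin D, a rising level can reveal that breach, and capsule counts cannot. For a control, that breach could shift PTH, whereas a missed inert capsule should not. This stands, and the fix must keep it.

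**A 25-OHD-based analysis suits the hypothesis.** The trial asks whether repletion lowers PTH, so PTH by attained level is worth reporting. That stands too, but it is not a per-protocol estimate in compliant patients. The threshold of 30 recurs often enough to be the obvious cut-off, so the missing rule is partly a wording gap. Stating 30 would still not make the marker a measure of compliance.

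**The time-course sentence is loosely worded.** Calling the covariate time-dependent only makes sense with repeated measures. The next sentence introduces mixed models, and the Cox safety model uses time-dependent dosage properly. A longitudinal model was probably intended. However, the text says the 6-month analysis is repeated, and the listed mixed-model terms omit intake. A reader might infer that the trial yields no PTH time course at all; that is wrong, since regimen by time gives the randomised one. A reader might also suppose that a 6-month intake slope would be projected back along the dosing calendar; the plan states no such step.

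**The magnitudes are assumed.** This is fair. The SD 7, baseline-mean-20 case puts about 9% of full compliers above 50 ng/ml, whereas the cited study had none. Season and weight, plausible sources of correlation between 25-OHD and PTH, are planned covariates. The supplied text also refers to a Data and Safety Monitoring section that is not included, and visit or adherence details may be there.

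**Conclusion.** The point holds, limited to two secondary analyses. The primary ITT analysis and N=40 are unaffected.

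(a) The per-protocol set is mislabelled. It selects on a post-randomisation response and cannot show placebo-capsule intake. Under assumed inputs, misclassification of full compliers is roughly 3-33%, or 0-58% at fixed baselines of 10 to 25. These figures depend on an assumed cut-off of 30, assumed baseline and rise distributions, and response proportional to intake in the half-intake cases. The structural argument does not depend on them. A reader might infer a seriously inflated treatment effect, but the calculation does not support that: the bias under no effect is 0-7% on the log scale, at most about 5% with baseline adjustment at an assumed correlation of 0.7, and zero if PTH is unrelated to 25-OHD within arm.

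(b) As written, the as-treated time course cannot be estimated. This follows from the design of the analysis and needs no assumption. The collinearity figures do rest on assumed adherence.

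Both should be corrected before unblinding.

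**What to change.** **(a)** Define the per-protocol set by recorded capsule intake plus no recorded use of non-study vitamin D. Apply one rule to both arms, fix it before unblinding, use the primary ANCOVA covariates, and label the result a non-randomised comparison. Keep PTH by attained 25-OHD as a separately labelled exploratory exposure-response analysis. Use 25-OHD in controls only as a check for outside vitamin D.

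**(b)** Fit the as-treated analysis in the planned repeated-measures mixed model with cumulative intake up to each visit. Name the coefficient to be reported and label it exploratory. Take the randomised time course from regimen by time.

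**Cost.** Low: mainly wording, plus naming the intake record. The planned cumulative-intake analysis already needs such data, but the supplied text names no source; if none is collected, one must be added. The downside is that an intake-based set is still a post-randomisation selection and is only as good as the intake records.

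### The secondary as-treated PTH model names no time term, so gradual PTH change shared by both arms is partly or wholly credited to vitamin D

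*Combined protocol and SAP*

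**What the plan says.** All of the relevant analysis text is in the Statistical Procedures section.

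- The primary analysis is a 6-month ANCOVA of "log-transformed serum PTH level adjusted for baseline serum PTH and the covariates listed below".
- The as-treated analysis is built on it. The primary analysis is run again "with actual cumulative vitamin D intake entered as a continuous time-dependent covariate to estimate the time course of the" as-treated PTH decrease.
- The covariate list is given once: "Standard covariates for all analyses include season, weight, serum calcium and age". Time and visit are not on it.
- Time is named for a separate longitudinal mixed model, which is "to assess the fixed effects of vitamin-D repletion regimen, time, regimen time interaction". The exposure there is randomized regimen, not cumulative intake.

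Study Design adds two things that both arms share from the start: "All subjects will receive 400 IU of vitamin D each day", and advice to take "up to 500 mg of supplemental calcium but no additional vitamin D".

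**The concern.** Cumulative intake can only go up. In a patient who follows the schedule it behaves almost like a clock. If the model has no time term, the intake coefficient has to explain whatever happens to PTH between visits, whether or not vitamin D caused it. Slow assay drift, slow change in the disease or a slow response to the calcium supplement would appear as a dose effect.

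The placebo arm is there to show what PTH does without repletion. In this model its 8 patients cannot do that job, because there is no common time course for them to inform. Keeping regimen in the model does not help. It takes out the average difference between arms and leaves the slope resting even more on change within the treated arm. The problem arises with perfect compliance and no withdrawals, so it is separate from confounding of intake by who stops treatment.

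At stake is the estimate of how far PTH falls with vitamin D actually taken, in a trial meant to inform treatment recommendations.

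**Working it through.** **The plan's own figure.** The plan gives no figure for this analysis. Its sample size does reproduce. The harmonic mean is 2×32×8/40 = 12.8, which rounds to 13. With ln(149/85) = 0.561 and log SDs of 0.411 and 0.526, from √ln(1+CV²), an unequal-variance t-test has 85.3% power at 32 vs 8. Eight is the smallest control group that reaches 80% at 4:1. The present point does not depend on this.

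**Is intake a clock?** From the Study Design schedule at full adherence, taking the first month as 4 weeks and counting the 400 IU daily (2,800 IU a week):

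| Week | Control, IU | Treated, IU |
|---|---|---|
| 4 | 4×2,800 = 11,200 | 11,200 + 4×20,000 = 91,200 |
| 13 | 13×2,800 = 36,400 | 36,400 + 80,000 + 9×10,000 = 206,400 |
| 26 | 26×2,800 = 72,800 | 72,800 + 80,000 + 22×10,000 = 372,800 |

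With some variation in adherence, the correlation of intake with time is 1.00 in controls and 0.98–0.99 in treated patients.

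**What a shared fall does to the slope.** Take a 10% fall in both arms, ln(0.9) = −0.105, linear over 26 weeks, with no vitamin D effect. From week 4 to week 26 log PTH moves by −0.105×22/26 = −0.089, while treated intake rises by 372,800 − 91,200 = 281,600 IU. A slope taken from the treated arm alone, times full intake, is −0.089×372,800/281,600 = −0.118. That is about the whole shared change. The simulated value is −0.10 to −0.13.

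**Why shape matters.** Baseline PTH is a covariate, so the outcomes are post-baseline values, and only change after the first of them can load on intake. With the first visit at month 1, the change still to come is:

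- linear fall: 0.105×5/6 = 0.088
- levelling off with a 1-month time constant: 0.105×(e⁻¹ − e⁻⁶) = 0.105×0.365 = 0.038
- step complete by month 1: 0

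**Simulated trials.** The setting is 32 vs 8, zero vitamin D effect, full compliance, log SD 0.41 (from 149 ± 64) and within-patient correlation 0.7. Models were fitted by GLS with compound symmetry, with a two-sided 5% test of the intake slope. Ranges cover regimen in or out of the model and 400 IU counted or not. Drift, visit times and correlation are assumptions.

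| Shared change, no time term | Visits at months | False rejection |
|---|---|---|
| None | 1, 3, 6 | 4–6% |
| 5% linear | 1, 3, 6 | 11–12% |
| 10% linear | 1, 3, 6 | 27–40% |
| 20% linear | 1, 3, 6 | 82–93% |
| 10% linear | 3, 6 | 11–16% |
| 10% linear | monthly | 35–50% |
| 10%, levels off | 1, 3, 6 | 10–14% |
| 10%, levels off | 3, 6 | 4–5% |
| 10% or 20% step before first visit | all tried | 4–8% |

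For the 10% linear fall with visits at months 1, 3 and 6, correlations of 0.5, 0.8 and 0.9 give 22–26%, 42–53% and 73–84%. With categorical visit added, rejection returns to 4–6% and the slope to about zero.

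A second method gives the same picture: exchangeable GEE with mean adherence 92%. A shared drift of −0.10 log units gave slopes of −0.085 to −0.099 per 300,000 IU and 40–53% rejection. With visit as a factor the slopes were −0.002 to 0.002. GEE rejection then stayed at 7–13%, against 6–10% with no drift, which is small-sample inflation of that method.

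**The case against.** A reader might infer that any PTH drift shared by both arms, regression to the mean included, is booked to vitamin D. The plan's own baseline adjustment rules that out. Change complete by the first post-baseline visit goes into the intercept, and in trials that selected patients on high baseline PTH the no-time model rejected in 4–6%. The highest rates belong to a fall that stays linear for 6 months, and the documents give no reason to expect that shape from calcium started at the first visit. If the 400 IU is counted as intake, crediting its effect to vitamin D is not misattribution. Season, if coded per visit, may absorb some drift; the simulations left out season, weight, serum calcium and age. All of this stands and limits the claim to gradual change.

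A reader might also infer that the plan excludes time from this model. It does not; it is silent. If only the 6-month value were modelled, shared drift would go into the intercept (4.6–6% rejection). That reading fits poorly with a time-dependent covariate and the aim of a time course. The next sentence names time for the mixed model, so its absence here leaves the analyst free to fit the biased version.

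Finally, the analysis is secondary and aims at estimation, with no decision tied to a test of the slope. This lowers the severity. It does not remove the point, because the estimate itself is biased by about the size of the shared fall when that fall is linear.

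**Conclusion.** The point holds in a limited form. Fitted from the terms the plan lists, the as-treated model credits to vitamin D, in part or in whole, PTH change that both arms share and that continues after the first post-baseline visit. The inflation is large for a sustained linear fall, modest for one that levels off within the first months, absent for an early step, and smaller with fewer visits. These sizes rest on assumed drift, visit times and correlation; the plan states no expected placebo change.

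Nothing here bears on the primary 6-month ANCOVA or on the mixed model that already includes time. It would be wrong to conclude that the trial's main PTH comparison is unsound. Minor severity; a cheap improvement.

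**What to change.** Add one sentence to Statistical Procedures: the as-treated PTH analysis is a repeated-measures model with a patient random intercept and with visit as a categorical fixed effect common to both arms. Equivalently, add cumulative intake to the mixed model that already has time. State that no intake slope will be reported from a model without the visit term.

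This needs no new data or patients. The cost is a wider interval for the intake slope, which then rests largely on the contrast with 8 controls. That width reflects the information the design really holds on this question.

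### The longitudinal mixed models do not use each measure's own baseline efficiently, which costs some precision on the secondary curves

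*Combined protocol and SAP*

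**What the plan says.** All references are to the combined protocol and SAP.

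- **Primary analysis (Statistical Procedures).** The 6-month endpoint is an ANCOVA of "between group differences in log-transformed serum PTH level adjusted for baseline serum PTH and the covariates listed below". This is the only analysis said to adjust for the outcome's own baseline.
- **Longitudinal analysis (same section).** "Analysis of the longitudinal growth curve of each" measure is to use "linear mixed models for repeated measures to assess the fixed effects of vitamin-D repletion regimen, time, regimen time interaction", with "random effects for intercept and standard covariates; and a covariance structure fit prior to the hypothesis test". I read this as a random intercept with the covariates as fixed effects.
- **Covariates (same section).** "Standard covariates for all analyses include season, weight, serum calcium and age". The Cox sentence calls such covariates time-independent: "adjusted for standard timeindependent covariates and time-dependent cumulative vitamin D dosage".
- **Measures concerned (Study Design).** The trial will "assess the changes in serum and urinary calcium, 25-OHD and 1,25-OH₂D among groups". The same section says that the six-month design is meant to follow the groups from before repletion through it. Allocation is randomised in permuted blocks.

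The plan does not say whether the baseline visit is a response in the mixed models, how time is coded, or which contrast will be reported. It also does not say that the randomised arms share a baseline mean.

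**The concern.** Randomisation makes the arms equal in expectation at time 0. A model with a free regimen main effect does not use that fact: it estimates a separate baseline mean for each arm and measures the effect as the departure from it. The regimen-by-time contrast then subtracts the whole observed baseline difference, when only a fraction rho of it is expected to persist. The standard covariates do not help with this contrast, because main effects that stay constant over time cancel out of a within-patient comparison when data are complete.

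If baseline is kept out of the response, the subtraction disappears, but so does any adjustment for a measure's own starting value. Serum calcium is the exception, because it is on the covariate list.

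What is at stake is the width of the intervals for urinary calcium, 1,25-OH2D, 25-OHD, serum calcium and the PTH curve, and how far a chance imbalance moves those estimates. The control arm has 8 patients, so imbalance is to be expected.

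**Working it through.** **The plan's own figure.** The plan gives no precision target for the longitudinal models. Its only related figure is the sample size. The harmonic mean is 2 x 32 x 8 / 40 = 12.8, stated as 13 per group. The log difference is ln(149/85) = 0.561. The log SDs, from sqrt(ln(1 + CV^2)), are 0.411 (64/149) and 0.526 (48/85). If controls stay at 149 (SD 64), a two-sided t-test at 0.05 with 13 per group has 82.8% power, so the figure reproduces. It rests on post-treatment PTH only, so the present point does not touch it.

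**Inputs.** Arms of 32 and 8 (Statistical Procedures). Assumed: equal variance s^2 at baseline and month 6, correlation rho between them, complete data, categorical time. Rho is not in the documents; 0.3 to 0.9 is shown. Write k = 1/32 + 1/8 = 0.15625.

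**Variance of the month-6 effect estimate (large sample)**

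- Baseline in the response, arms free at baseline: 2(1 - rho) s^2 k
- Baseline left out: s^2 k
- Baseline-adjusted, or common baseline mean: (1 - rho^2) s^2 k

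The first over the third is 2/(1 + rho). The second over the third is 1/(1 - rho^2).

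| rho | 2/(1+rho) | Interval wider by | Effective N of 40 | Power if the adjusted analysis has 80% | 1/(1-rho^2) |
|---|---|---|---|---|---|
| 0.3 | 1.54 | 24% | 26 | 62% | 1.10 |
| 0.5 | 1.33 | 15% | 30 | 68% | 1.33 |
| 0.7 | 1.18 | 8% | 34 | 73% | 1.96 |
| 0.9 | 1.05 | 3% | 38 | 78% | 5.26 |

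Columns three to five refer to the change contrast: the square root of the ratio minus 1; 40 divided by the ratio; and power with the noncentrality divided by the square root of the ratio.

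**Small-sample check.** Estimating the baseline slope costs ANCOVA a factor of about 1 + 1/36 = 1.03 at N = 40. Simulated trials of 32 versus 8 agree: the change contrast gave 1.50, 1.30, 1.15 and 1.02 at the four correlations, and leaving baseline out gave 1.06, 1.31, 1.91 and 5.13. Where means were checked, at rho 0.5, the change and ANCOVA estimators were both unbiased.

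**Does the planned model reduce to a change comparison?** In mixed models fitted to complete simulated data, the regimen-by-time estimate equalled the difference in mean change to rounding error. Adding a time-constant covariate did not move it (-0.5636 with and without). In another data set the change contrast was -0.361, against -0.242 for ANCOVA and -0.250 for the common-baseline model.

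**Time coded linearly.** With a random intercept and four trial visit schedules (months 0/6, 0/3/6, 0/1/3/6, and monthly), the ratio is 1.44 to 1.66 at rho 0.3, 1.24 to 1.38 at 0.5, 1.12 to 1.19 at 0.7, and 1.03 to 1.05 at 0.9.

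**Chance imbalance.** The baseline difference between arms has standard error sqrt(0.15625) = 0.40 SD. It exceeds 0.3 SD in either direction with probability 2 x [1 - Phi(0.3/0.395)], about 45%. Given a baseline difference d, the change contrast has expectation (effect) + rho d - d, so it is displaced by -(1 - rho)d. At rho 0.5 that is half the imbalance.

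**The case against.** The planned model is standard and valid under randomisation, and the stated aim is to compare changes, so a change contrast answers the question as written. That stands: the point is about efficiency. A reader might infer from the displacement above that the model is biased. It is not. The displacement is conditional on an observed imbalance and averages to zero over randomisations.

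A reader might also infer that the trial's safety conclusions depend on these models. The documents do not support that. Event rates go to Fisher's exact tests and a Cox model for time to first AE. The counts above 400 mg/day and the event frequencies at each time point are likewise compared outside the mixed models. Only the continuous calcium trajectories are affected. Nor is the main PTH result exposed, because its ANCOVA already adjusts for baseline.

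Two premises are likely but not stated. The growth-curve wording and the before-and-during design suggest that baseline is a response, but the plan does not say so. The covariates are called time-independent only in the Cox sentence, the list is open-ended, and season, weight and serum calcium could be updated by visit. Withdrawals would also make the cancellation approximate. These caveats limit the exact algebra but do not remove the point. Under either reading of baseline, the stated list does not supply the baseline of urinary calcium, 1,25-OH2D, 25-OHD or PTH.

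Finally, the size rests wholly on assumed correlations. At rho 0.8 to 0.9 the change contrast widens intervals by only about 3% to 5%. That is fair, although it is where leaving baseline out costs most.

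**Conclusion.** The point holds as a modest, avoidable loss of precision on the secondary continuous curves, together with sensitivity to chance baseline imbalance when there are 8 controls. If baseline is in the response, intervals are about 3% to 24% wider for rho from 0.9 down to 0.3. If it is left out, the variance ratio runs from about 1.10 to 5.26 over the same range in the opposite direction, except for serum calcium.

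These figures assume equal variances at the two times, complete data and correlations that the documents do not give. Time coding and visit schedule are also unstated. The change is worth making because it uses a baseline value that the trial collects anyway and extends to the secondary measures what the primary ANCOVA already does.

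**What to change.** In each longitudinal model, do one of the following and say which:

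1. Keep the baseline visit in the response and constrain the randomised arms to a common baseline mean: visit plus regimen by post-baseline visit, with no regimen main effect.
2. Model post-baseline visits only, with the measure's own baseline by visit as a covariate.

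The two are nearly equivalent and differ in how they handle missing values. Name the month-6 regimen difference as the reported contrast, and state whether the standard covariates are baseline values.

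When serum calcium is the outcome and its baseline is already in the response, do not enter baseline serum calcium again as a covariate. With complete data and time-constant covariates, that double entry would not move the regimen-by-time contrast in the planned model, so this is tidying that goes with the rewrite and not a separate defect.

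The cost is a few sentences in Statistical Procedures and a few lines of code. No new data or patients are needed, and the primary analysis does not change.
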